4. PATIENT SELECTION

4.1 Inclusion criteria

For inclusion in the study patients must fulfill all of the following criteria:

1. Patients with pathologically documented NSCLC who are deemed to be candidates for definitive surgery: Stage will be categorized based on 8th edition of American Joint Committee on Cancer (AJCC) Non-small cell Lung Cancer Staging system; see Appendix 3.
2. Capable of giving signed informed consent which includes compliance with the requirements and restrictions listed in the informed consent form (ICF) and in this protocol. Written informed consent and any locally required authorization (eg, Health Insurance Portability and Accountability Act in the US) obtained from the patient/legal representative prior to performing any protocol-related procedures, including screening evaluations.
3. Age ≥ 18 years at time of study entry.
4. Eastern Cooperative Oncology Group (ECOG) performance status of 0 or 1
5. Life expectancy of ≥ 26 weeks
6. Body weight >30 kg
7. Adequate normal organ and marrow function as defined below:
 - Haemoglobin ≥ 9.0 g/dL
 - Absolute neutrophil count (ANC) $1.5 \times 10^9/L$ (≥ 1500 per mm 3)
 - Platelet count $\geq 100 \times 10^9/L$ ($\geq 100,000$ per mm 3)
 - Serum bilirubin $\leq 1.5 \times$ institutional upper limit of normal (ULN).
 - AST (SGOT)/ALT (SGPT) $\leq 2.5 \times$ institutional upper limit of normal unless liver metastases are present, in which case it must be ≤ 5 x ULN
 - Measured creatinine clearance (CL) >40 mL/min or Calculated creatinine CL >40 mL/min by the Cockcroft-Gault formula (Cockcroft and Gault 1976) or by 24-hour urine collection for determination of creatinine clearance:

Males:

$$\text{Creatinine CL} = \frac{\text{Weight (kg)} \times (140 - \text{Age})}{72 \times \text{serum creatinine (mg/dL)}}$$

Females:

$$\text{Creatinine CL} = \frac{\text{Weight (kg)} \times (140 - \text{Age})}{72 \times \text{serum creatinine (mg/dL)}} \times 0.85$$

8. Evidence of post-menopausal status or negative urinary or serum pregnancy test for female pre-menopausal patients. Women will be considered post-menopausal if they have been amenorrheic for 12 months without an alternative medical cause. The following age-specific requirements apply:
 - Women <50 years of age would be considered post-menopausal if they have been amenorrheic for 12 months or more following cessation of exogenous hormonal treatments and if they have luteinizing hormone and follicle-stimulating hormone levels in the post-menopausal range for the institution or underwent surgical sterilization (bilateral oophorectomy or hysterectomy).
 - Women ≥50 years of age would be considered post-menopausal if they have been amenorrheic for 12 months or more following cessation of all exogenous hormonal treatments, had radiation-induced menopause with last menses >1 year ago, had chemotherapy-induced menopause with last menses >1 year ago, or underwent surgical sterilization (bilateral oophorectomy, bilateral salpingectomy or hysterectomy).
9. Patient is willing and able to comply with the protocol for the duration of the study including undergoing treatment and scheduled visits and examinations including follow up.
10. Patients must consent to pre-treatment research biopsy and study peripheral blood collection.
11. Patients must have measurable disease, defined by RECIST v 1.1.
12. Patient is able to take oral medications
13. Patient consents to heavy water (D2O) self-administration if on optional heavy water labelling study

4.2 Exclusion criteria

Patients should not enter the study if any of the following exclusion criteria are fulfilled:

1. Patients who have had prior therapy for lung cancer including chemotherapy, hormonal therapy, or radiotherapy.
2. Concurrent enrolment in another clinical study, unless it is an observational (non-interventional) clinical study
3. Prior treatment with anti-PD-1, anti-PDL-1, including durvalumab other PD-1/PDL-1 pathway targeting agents, or mTOR inhibition.
4. History of allogenic organ transplantation.
5. Active or prior documented autoimmune or inflammatory disorders (including inflammatory bowel disease [e.g., colitis or Crohn's disease], systemic lupus erythematosus, Sarcoidosis syndrome, or Wegener syndrome [granulomatosis with polyangiitis, Graves' disease, rheumatoid arthritis, hypophysitis, uveitis, etc]). The following are exceptions to this criterion:
 - a. Patients with vitiligo or alopecia
 - b. Patients with hypothyroidism (e.g., following Hashimoto syndrome) stable on hormone replacement
 - c. Any chronic skin condition that does not require systemic therapy
 - d. Patients without active disease in the last 5 years may be included but only after consultation with the study physician
 - e. Patients with celiac disease controlled by diet alone
6. Uncontrolled intercurrent illness, including but not limited to, ongoing or active infection, symptomatic congestive heart failure, uncontrolled hypertension, unstable angina pectoris, cardiac arrhythmia, interstitial lung disease, serious chronic gastrointestinal conditions associated with diarrhea, or psychiatric illness/social situations that would limit compliance with study requirement, substantially increase risk of incurring AEs or compromise the ability of the patient to give written informed consent
7. History of another primary malignancy except for

- a. Malignancy treated with curative intent and with no known active disease ≥ 5 years before the first dose of IP and of low potential risk for recurrence
- b. Adequately treated non-melanoma skin cancer or lentigo maligna without evidence of disease
- c. Adequately treated carcinoma in situ without evidence of disease

8. QT interval corrected for heart rate using Fridericia's formula (QTcF) ≥ 470 ms. Patient safety and the cardiac SKG should be consulted as needed.

9. History of active primary immunodeficiency

10. Active infection including **tuberculosis** (clinical evaluation that includes clinical history, physical examination and radiographic findings, and TB testing in line with local practice), **hepatitis B** (known positive HBV surface antigen (HBsAg) result), **hepatitis C**. Patients with a past or resolved HBV infection (defined as the presence of hepatitis B core antibody [anti-HBc] and absence of HBsAg) are eligible. Patients positive for hepatitis C (HCV) antibody are eligible only if polymerase chain reaction is negative for HCV RNA.

11. Current or prior use of immunosuppressive medication within 14 days before the first dose of durvalumab. The following are exceptions to this criterion:

- a. Intranasal, inhaled, topical steroids, or local steroid injections (e.g., intra articular injection)
- b. Systemic corticosteroids at physiologic doses not to exceed 10 mg/day of prednisone or its equivalent
- c. Steroids as premedication for hypersensitivity reactions (e.g., CT scan premedication)

12. Receipt of live attenuated vaccine within 30 days prior to the first dose of IP. Note: Patients, if enrolled, should not receive live vaccine whilst receiving IP and up to 30 days after the last dose of IP.

13. Female patients who are pregnant or breastfeeding or male or female patients of reproductive potential who are not willing to employ effective birth control from screening to 90 days after the last dose of durvalumab monotherapy.

14. Known allergy or hypersensitivity to any of the study drugs or any of the study drug excipients.

Clinical Study Protocol

Investigational Drug Substance: MEDI4736 Sirolimus (Rapamune)

Study Number **19-20015**

Edition Number: 4

Date: **11 February 2022**

15. Prior randomisation or treatment in a previous durvalumab clinical study regardless of treatment arm assignment.
16. Patients with a history of idiopathic pulmonary fibrosis, pneumonitis (including drug induced), organizing pneumonia, or evidence of active pneumonitis on screening chest CT scan
17. Inability to stop prohibited concomitant medications listed in Section 7.7.2.
18. Judgment by the investigator that the patient is unsuitable to participate in the study and the patient is unlikely to comply with study procedures, restrictions and requirements.

Procedures for withdrawal of incorrectly enrolled patients are presented in Section 4.3

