Edition Number: **4**

Date: **11 February 2022**

- To evaluate the efficacy of sirolimus followed by durvalumab as neoadjuvant treatment for Stage I, II, and IIIA NSCLC

Secondary Objective(s):

- To evaluate the efficacy of sirolimus followed by durvalumab as neoadjuvant treatment for Stage I, II, and IIIA NSCLC
- To evaluate response to sirolimus followed by durvalumab in patients with PD-L1 positive vs. PD-L1-negative tumors
- To evaluate the association between blood mutation burden and response to sirolimus followed by durvalumab

Exploratory Objective(s):

- To evaluate the immune-mediated effects of sirolimus followed by durvalumab
- To investigate tumor and immune microenvironment changes in tissue samples

Study Design:

Up to 31 patients with NSCLC will be enrolled in this study at Emory University Winship Cancer Institute and associated clinical sites. Eligible patients will complete 3 weeks of daily oral sirolimus followed by 2 cycles of durvalumab treatment prior to proceeding to standard of care surgical resection. Durvalumab will be administered at a dose of 1500mg Q 3 weeks starting on C1D1 for up to 2 cycles that are 21 days in length. Pharmacodynamic analysis will be done using PD samples collected at baseline (tissue) and with blood samples on day 1, day 22 C1 prior to durvalumab, day 43 C2 durvalumab, and at the time of surgery (blood and tissue). Additional post surgery blood samples will be collected at 1-, 3-, and 6-months post-surgery. See Appendix D for schedule of Biomarker collection. Patients will proceed to surgery within a 2–3-week period post 2nd dose of durvalumab but not earlier than two weeks after the administration of durvalumab i.e. not earlier than C2D14. Additionally, as an optional study, patients will self-administer heavy water (D2O) 50ml orally three times a day from day 22 C1 through day 27 followed by 50ml orally twice a day through the day prior to surgery in order to label dividing cells for research tracking purposes.

Number of Centers: Emory University Winship Cancer Institute and affiliated hospitals

Number of Patients: 31

Study Population: Resectable Stage 1-3A NSCLC

Inclusion Criteria:

- Pathologically documented NSCLC who are candidates for surgical resection
- Capable of signing informed consent

- Age \geq 18 years at time of study entry.
- Eastern Cooperative Oncology Group (ECOG) performance status of 0 or 1
- Life expectancy of \geq 26 weeks
- Body weight >30 kg

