- Adequate normal organ and marrow function as defined in protocol
- Evidence of post-menopausal status or negative urinary or serum pregnancy test for female pre-menopausal patients.
- Measurable disease defined by RECIST v 1.1.
- Patient is able to take oral medications
- Patient consents to heavy water (D2O) self-administration, if enrolling in optional heavy water study
- Patient is willing and able to comply with the protocol for the duration of the study including undergoing treatment and scheduled visits and examinations including follow up.

Exclusion Criteria:

- Prior therapy for lung cancer including chemotherapy, hormonal therapy, or radiotherapy.
- Concurrent enrolment in another clinical study, unless it is observational
- Prior treatment with anti-PD-1, anti-PDL-1, including durvalumab other PD-1/PDL-1 pathway targeting agents, or mTOR inhibition.
- History of allogenic organ transplantation.
- Active or prior documented autoimmune or inflammatory disorders (including inflammatory bowel disease [e.g., colitis or Crohn's disease], systemic lupus erythematosus, Sarcoidosis syndrome, or Wegener syndrome [granulomatosis with polyangiitis, Graves' disease, rheumatoid arthritis, hypophysitis, uveitis, etc]). Exceptions listed in protocol below.
- Uncontrolled intercurrent illness
- History of another primary malignancy with exceptions noted in protocol
- QT interval corrected for heart rate using Fridericia's formula (QTcF) \geq 470 ms
- History of active primary immunodeficiency
- Active infection including tuberculosis, hepatitis B, hepatitis C
- Current or prior use of immunosuppressive medication within 14 days before the first dose of durvalumab. There are exceptions to this criterion listed below in the protocol
- Receipt of live attenuated vaccine within 30 days prior to the first dose of study medications

- Female patients who are pregnant or breastfeeding or male or female patients of reproductive potential who are not willing to employ effective birth control from screening to 90 days after the last dose of durvalumab
- Known allergy or hypersensitivity to any of the study drugs or excipients.
- Patients with a history of idiopathic pulmonary fibrosis, pneumonitis (including drug induced), organizing pneumonia, or evidence of active pneumonitis on screening chest CT scan

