Useful but not entirely predictive or prognostic markers established to date include PD-L1 expression on the tumor and tumor mutation burden. Comparison across trials of PD-L1 expression is complicated by different companion diagnostic tests that have been developed along with technical variables including biopsy source, processing, detection antibodies, and immunohistochemistry cutoffs¹⁷. In general, patients with higher tumor PD-L1 expression showed improved response rates and overall survival compared to patients with low PD-L1 expression¹⁸. However, patients with low or no PDL-1 expression can still derive a benefit, and therefore other markers are being studied. Interestingly, the number of mutations identified in the tumor may predict response. Rizvi et al. demonstrated with whole exome sequencing that improved response rates and PFS were seen in patients with higher mutational burdens treated with pembrolizumab¹⁹. Similar findings were seen using next generation sequencing of patients treated with PD-1 or PD-L1 directed monotherapy or combination immunotherapy²⁰. The development of reliable biomarkers would further improve the ability to interrogate the effectiveness of combination therapies in both preclinical and clinical studies.

Ideal agents to combine with PD-1/PDL-1 checkpoint inhibitor therapy would include well-tolerated, easy to administer drugs with single agent anti-cancer activity that have a complementary effect on the immune system. The mammalian target of rapamycin (mTOR) is one such therapeutic target in cancer based on its diverse roles in cell proliferation, metabolism, and survival. There are currently three FDA approved inhibitors of mTOR: rapamycin (sirolimus) and two rapamycin analogs or rapalogs, everolimus and temsirolimus. Sirolimus has long been used as an immunosuppressant in organ transplantation, temsirolimus is approved for use in renal cell carcinoma²¹ and everolimus has FDA indications for multiple solid organ malignancies including the treatment of hormone receptor positive HER-2 negative breast cancer, neuroendocrine tumors of the pancreas²², lung, or GI tract, and renal cell carcinoma (RCC)²³. Additionally, single agent neoadjuvant everolimus was tested in resectable NSCLC. In this window of opportunity study 23 patients were treated with everolimus (5 or 10mg daily) for 3 to four weeks, followed by resection, with evidence of dose dependent, metabolic, and anticancer activity²⁴.

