The dose of sirolimus chosen for this study is based on our pre-clinical data that indicate that a lower dose is most likely to result in the desirable pharmacodynamics effects on the immune system. For clinical use in the renal transplant setting and high immunologic risk transplants, sirolimus is recommended at an initial loading dose of 15 mg followed by 5mg/day maintenance, with adjustments based on trough level. In lymphangiomyomatosis (LAM), the recommended dose is 2 mg daily to block mTOR pathway activation; median whole blood

Date: **11 February 2022**

sirolimus trough concentration after 3 weeks of receiving sirolimus tablets at a dose of 2 mg/day was 6.8 ng/mL (interquartile range 4.6 to 9.0 ng/mL; n = 37). As the sirolimus treatment phase will be only 3 weeks, a single loading dose of 6mg on day 1 will be followed by 2mg daily. No dose changes will be made for individual patients given this short term low dose regimen designed to reach levels of 5-15 ng/ml, which was noted in pre-clinical studies to correlate with proliferation of memory T cells. This lower dose is also likely to be tolerated better by patients.

As an added safety measure, the first 6 patients will be monitored through hospital discharge following surgical resection to assess for dose limiting toxicities (DLTs) related to sirolimus followed by durvalumab therapy. DLTs and safety analysis are described in section 6.4.

Patients will be closely monitored for safety and tolerability throughout the study. Safety assessments will include collection and monitoring of adverse events and laboratory abnormalities graded per the National Cancer Institute Common Terminology Criteria for Adverse Events, Version 5.0 (NCI CTCAE v5.0). Tumor tissue samples, normal lung parenchyma, whole blood samples, and optional lymph node samples will be collected for biomarker assessments.

After study treatment discontinuation, patients will be followed per SOC, but information on recurrence and survival will be collected every 6 months for up to 2 years after the last patient receives the last dose in the study (in person or by phone). Patients who discontinue the study due to adverse events will be followed until resolution or stabilization of the adverse event. Appropriate dose modifications are described in Section 6. No investigational or commercial agents or therapies other than those described below may be administered with the intent to treat the patient's malignancy.

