5.2.2 Doses and treatment regimens

The dose of sirolimus for this study is 6mg orally daily once on day 1, followed by 2mg orally daily from day 2 through 21.

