8.1.1 Screening phase

Screening procedures will be performed up to 35 days before Day -7, unless otherwise specified. All patients must first read, understand, and sign the IRB approved ICF before any study-specific screening procedures are performed. After signing the ICF, completing all screening procedures, and being deemed eligible for entry, patients will be enrolled in the study. Procedures that are performed prior to the signing of the ICF and are considered standard of care may be used as screening assessments if they fall within the 28-day screening window.

The following procedures will be performed during the Screening Visit:

- Informed Consent
- Review of eligibility criteria
- Medical history and demographics
- Complete physical exam
- ECOG Performance Status
- Vitals signs, weight and height

- 12-lead ECG (in triplicate [2-5 minutes apart])
- Tumor biopsy for fresh tissue if not already obtained
- Review of prior/concomitant medications
- Imaging by CT/MRI
- Clinical laboratory tests for:
 - Hematology (see Table 7)
 - Clinical chemistry (see Table 8)
 - TSH
 - Coagulation (PT, PTT, INR)
 - Creatinine Clearance
 - Serum pregnancy test (for women of childbearing potential only)
 - Hepatitis serologies
 - Urinalysis (see Table 9)

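### Exclusion 11 dates its 14-day immunosuppressant look-back from durvalumab, so the window falls after enrollment, overlaps unexempted protocol sirolimus, and sets no washout before sirolimus day 1

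*Combined protocol and SAP*

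**What the plan says.** Section 4.2, exclusion 11, excludes patients with "Current or prior use of immunosuppressive medication within 14 days before the first dose of durvalumab". Its three exceptions all concern steroids: non-systemic or local use, physiologic systemic doses, and premedication for hypersensitivity. The synopsis has the same rule and adds "There are exceptions to this criterion listed below in the protocol".

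The rule decides entry. Section 4.2 opens with "Patients should not enter the study if any of the following exclusion criteria are fulfilled", and Section 8.1.1 fixes the moment: "After signing the ICF, completing all screening procedures, and being deemed eligible for entry, patients will be enrolled in the study".

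Treatment starts with sirolimus. Section 5.2.2 gives 6 mg on day 1, "followed by 2mg orally daily from day 2 through 21". Durvalumab follows on day 22 (Section 8.1.2), with a window of ± 3 days in the Schedule of Study Assessments. Section 1.1.1 says "Sirolimus has long been used as an immunosuppressant in organ transplantation".

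The neighbouring dated exclusions, 7a and 12, count back from the first dose of investigational product. Table 11 in Section 15.1 lists sirolimus as one, so those rules are dated from sirolimus day 1.

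**The concern.** An entry rule should be answerable when entry is decided. The dated part of exclusion 11 asks about days that have not yet happened, and those days are mostly or entirely sirolimus days under the protocol itself. The period that can be examined at screening, the two weeks before day 1, is left without a dated rule.

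What is at stake is the pre-sirolimus baseline. Section 3.1 explains that sirolimus is given alone first so that its contribution can be separated from durvalumab's. The synopsis schedules pharmacodynamic sampling "with blood samples on day 1, day 22 C1 prior to durvalumab", and Section 2.3 makes serial blood and tissue immune assessments an exploratory objective. If a patient has just stopped another immunosuppressant, the day 1 sample may reflect that drug, and so may any change measured from it.

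**Working it through.** **Inputs**
- Look-back: 14 days before the first durvalumab dose (Section 4.2, exclusion 11; synopsis).
- Sirolimus: days 1–21 (Section 5.2.2).
- First durvalumab dose, day D: 22 (Section 8.1.2) ± 3 (Schedule of Study Assessments), so D = 19 to 25.
- Enrollment: when screening is complete and eligibility is confirmed (Section 8.1.1), so before sirolimus starts.
- Numbering: the schedule runs from −28 to 0 and then 1–21, so day 0 is the day before day 1.

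**Step 1: the plan's own figure.** The last sirolimus day is 21, and 21 + 1 = 22, which matches the stated durvalumab start.

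**Step 2: where the window falls.** It covers days D − 14 to D − 1. The last column counts the days that are also sirolimus days 1–21.

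| Durvalumab day D | Look-back days | Sirolimus days inside |
|---|---|---|
| 19 | 5–18 | 14 of 14 |
| 20 | 6–19 | 14 of 14 |
| 21 | 7–20 | 14 of 14 |
| 22 | 8–21 | 14 of 14 |
| 23 | 9–22 | 13 of 14 |
| 24 | 10–23 | 12 of 14 |
| 25 | 11–24 | 11 of 14 |

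**Step 3: cover before sirolimus.** The 14 days before day 1 are days −13 to 0. The overlap with every window above is 0 of 14. To reach day 0 the window needs D − 14 ≤ 0, so D ≤ 14. The earliest permitted day is 19, which is 19 − 14 = 5 days too late. Any delay to durvalumab moves the window later still.

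**Step 4: a patient who stops during screening.** Let the last dose of a non-study immunosuppressant fall on day L. The gap to the day 1 sample is 1 − L. The gap to durvalumab is 19 − L to 25 − L. The margin over the rule is that gap minus 14.

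| Last dose L | Days before day 1 sample | Days before durvalumab | Clears the rule by |
|---|---|---|---|
| −1 | 2 | 20–26 | 6–12 days |
| −13 | 14 | 32–38 | 18–24 days |

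**Step 5: other provisions that might close the gap**
- 'Current' use, read on its own, catches a patient still taking the drug at the eligibility check, but not one who has already stopped.
- Exclusion 17 requires the ability to stop prohibited drugs and gives no interval.
- Table 5 (Section 7.2.2) restricts immunosuppressants during study treatment and sets no washout before it.
- Section 7.2 counts concomitant therapy from 7 days before study drug. That is a definition for recording, not an eligibility rule.

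**Step 6: the primary design.** For the stated rule (continue with at least 2 responses in 16, succeed with at least 6 in 31), the chance of success is the sum over x = 2 to 16 of P(X₁ = x) × P(X₂ ≥ 6 − x), with X₁ binomial(16, p) and X₂ binomial(15, p). It is 0.079 at p = 0.10 and 0.805 at p = 0.25, in line with the stated alpha of 0.1 and power of 80%. Nothing in this calculation depends on exclusion 11.

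**The case against.** The durvalumab anchor has a sensible purpose: keeping other immunosuppressants away from the checkpoint inhibitor. Table 5 has the same focus. On that purpose the rule is not breached by the patients in question, since Step 4 puts them at least 20 days clear of durvalumab. The documents never say that exclusion 11 is meant to protect an exploratory sample. Ongoing use can still be checked at screening. Section 8.1.1 requires a review of prior and concomitant medications, so recent exposure can be identified and allowed for in analysis. Exclusions 3, 4 and 5 already remove prior mTOR-inhibitor users, transplant recipients and most patients with autoimmune disease. The exploratory analyses in Section 11.2.3 prespecify no test.

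Most of this stands, and it limits the importance of the point. It does not rescue the wording: the dated half of an entry criterion still cannot be applied at entry, and no other rule sets a washout before sirolimus. The objection also shows that simply moving the anchor would remove the only washout tied to durvalumab and leave days 1–21 to Table 5, which permits temporary steroid courses. The durvalumab-dated window should therefore be kept in another form.

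A reader might infer that, taken literally, every treated patient meets exclusion 11, because sirolimus is an immunosuppressant and is not among the exceptions. The documents do not support that as the intended meaning. The criterion governs entry, Section 5.2.2 mandates sirolimus, and Section 3.1 describes a "short term low dose regimen designed to reach levels of 5-15 ng/ml", a range chosen for its association with memory T cell proliferation. Sites are unlikely to exclude anyone on this ground. The missing exemption is a wording fault.

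**Conclusion.** The point holds and is minor. On every permitted schedule the dated look-back opens on day 5 to 11, covers 0 of the 14 days before sirolimus day 1, and is filled by protocol sirolimus for 11 to 14 of its 14 days.

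The consequence is confined to patients who stop a non-study immunosuppressant during screening and then give the day 1 sample. Their number is not stated and is likely small. A reader might infer that durvalumab's effect or the pCR result is compromised. The documents do not support that: these patients clear the 14 days before durvalumab by 6 to 24 days (last dose on day −13 to −1), and the pCR test, alpha, power and sample size do not change.

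The conclusion assumes that sirolimus is confined to days 1–21, that 'current' stands alone in the criterion, and that the baseline blood is taken on day 1, as the synopsis and schedule say. Section 3.1 still labels that sample day −7. Nothing in the documents shows that 14 days is the right washout for an immune baseline; the figure is carried over from the existing rule.

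**What to change.** In Section 4.2 and the synopsis, reword exclusion 11 along these lines:

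> Current use, or use within 14 days before the first dose of study drug (sirolimus day 1), of immunosuppressive medication other than protocol-assigned sirolimus.

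Keep exceptions a to c. The new window is days 1 − 14 = −13 to 0. It lies inside the day −28 to 0 screening period and matches the anchor of exclusions 7a and 12.

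Retain the durvalumab-dated window as a pre-dose check, not an entry criterion: no non-study immunosuppressant in the 14 days before the first durvalumab dose, outside exceptions a to c and Table 5's allowances. State what follows if the check fails. Section 8.1 already allows durvalumab to be delayed for reasons other than toxicity.

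Take a 14-day immunosuppressant history at the existing screening medication review, because the 7-day definition in Section 7.2 is too short for the new rule.

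The cost is one sentence in two places, one pre-dose check and a longer medication history. A few patients would be excluded or start later. With a last dose on day −1, that dose must come to lie on day −14, a delay of 13 days. An immunosuppressant course above the exceptions would count against entry shortly before day 1, whereas Table 5 may allow a steroid course after it. The change does not protect a biopsy taken earlier in screening. If day −7 were the true baseline, a permitted last dose on day −14 would be only 7 days before it, so the sampling day in Section 3.1 should be corrected at the same time.
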